8. EFFICACY MEASURES

8.1 SUBJECT COMPLIANCE

Compliance will be determined from the diary sheets. Subjects will record device and electroconductive media application and any comments on the

provided weekly diary. Diary sheets will remain at the study center as part of the source documentation records.

9. FINAL SUBJECT STATUS

A study termination form will be completed for each study subject who receives study product. This includes subjects who completed the study or who withdrew or were withdrawn from study.

9.1 COMPLETED, DISCONTINUED OR INCOMPLETE SUBJECTS

A completed subject is a subject who has satisfied all study entry criteria and completed the 12-week study. For any subject who has started study and terminated from the study prematurely, every effort will be made to obtain final evaluations of clinical status. Reasonable effort will be made to contact any subject lost to follow-up during the course of the study in order to complete assessments and retrieve any outstanding data and clinical supplies. The investigator will choose the description that best describes the status of the subject at termination.

1. Subject completed the 12 week study period

OR INCOMPLETE/DISCONTINUED DUE TO:

- 2. Contact dermatitis
- 3. Adverse experience
- 4. Serious adverse experience
- 5. Pregnancy
- 6. Protocol violation
- 7. Subject withdrew consent
- 8. Subject lost due to follow-up issues (e.g., attendance issues)
- 9. Other (provide reason)

10. STUDY PRODUCTS & ADMINISTRATION

10.1 FORMULATIONS

The study will consist of the ZIIP device programmed for the treatment of acne and the electroconductive media

10.2 PRECAUTIONS

Study products should be used as instructed and not orally consumed or placed in the eyes or around the orbital area of the eye. The device should be used as described below:

- 1. Begin with clean, dry skin.
- 2. Apply the conductive medium provided to you liberally over any areas where you have acne.
- 3. Turn on your device by pressing the button at the top. You will hear one beep.
- 4. Place the device on top of your skin. Lights will illuminate under the device when both silver probes come in contact with your skin. Both probes must keep contact with skin throughout treatment.
- 5. Follow along with the video, slowly making circles with the top probe (the one farthest away from the charging port) over acne within each zone. (You may feel a tingling sensation during treatment. That is normal.)
- 6. Do not treat a single spot more than one minute at a time. Only treat the facial zones identified for treatment.
- 7. At the end of treatment, your device will beep twice and turn off.
- 8. After treatment, wipe your device clean with a tissue, being careful to avoid the charging port. Spray the device and a second tissue lightly with rubbing alcohol and wipe again, remaining careful to avoid the charging port.
- 9. Store safely away from water, moisture or debris.

CHARGING:

When you see the orange light flashing while using your device, it's time to charge.

To charge, plug in the charging cable provided. The orange light will remain illuminated while charging. You will know that your device is completely charged when the orange light is no longer on.

CONTRAINDICATIONS

ZIIP should not be used in the following areas

- Breast area
- Directly on top of the eyelid
- Midline of neck (bone of neck)
- Groin area
- Do not use this device on patients who have a cardiac pacemaker, implanted defibrillator, or other implanted metallic or electronic device because this may cause electric shock

WARNINGS

Do not submerge the device in water or any other liquid(s). If you store your ZIIP in an area such as a bathroom counter, ensure the product does not come in contact with water or other liquid(s).

ZIIP should not be used by:

- Children
- Pregnant Women
- People subject to seizures
- People with cancer/tumors

- People with a cardiac pacemaker
- People with implanted defibrillators/stimulators
- People with electronic implanted devices

If you have any medical concerns, such as a severe medical illness, epilepsy or seizures, or recent facial surgery, please consult your doctor before using ZIIP.

Electronic monitoring equipment (such as ECG monitors and ECG alarms) may not operate properly when a ZIIP device is in use.

Stimulation should not be applied over, or in proximity to cancerous lesions, or applied over swollen, infected, or inflamed areas or skin eruptions, e.g., phlebitis, thrombophlebitis, broken capillaries, varicose veins, etc. Men should shave before use as hair can interfere with the conductivity of the electrodes. Facial area under a beard or mustache cannot be treated.

Do not apply stimulation across your chest as the introduction of electrical current into the chest may cause rhythm disturbances to your heart, which could be lethal.

The long-term effects of stimulation are not known.

10.3 STUDY PRODUCT ADMINISTRATION

Subjects will use the acne device for applied 3 days per week on non-consecutive days, on all facial zones afflicted by acne. The electroconductive media will be applied to the face prior to the use of the device. The following instructions will be provided:

- 1. Both silver probes must come in contact with skin throughout treatment.
- 2. Slowly make continuous circles with the top probe (the one farthest away from the charging port) over acne within each facial zone.
- **NOTE: Instructional video will be provided for participants to follow**
- 3. Treat each facial zone for 1 minute. Your device will beep and vibrate at the one minute mark to indicate that treatment of that zone is complete. Only treat the acne zone(s) identified for treatment.
- 4. After treatment, wipe your device clean with a tissue, being careful to avoid the charging port. Spray the device and a second tissue lightly with rubbing alcohol and wipe again, remaining careful to avoid the charging port.
- 5. Store safely away from water, moisture or debris.

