1. PROTOCOL SYNOPSIS

| Title of Study: | Evaluation of the Safety and Efficacy of an Acne Treatment Device |
|--|---|
| Study Period: | 12 weeks |
| Test Device and Application Instructions: | ZIIP Device (active) -400 microamps direct current, applied 3 days per week on non-consecutive days, on all areas afflicted by acne The following instructions will be provided: 1. Both silver probes must come in contact with skin throughout treatment. 2. Slowly make continuous circles with the top probe (the one farthest away from the charging port) over acne within each facial zone. **NOTE: Instructional video will be provided for participants to follow** 3. Treat each facial zone for 1 minute. Your device will beep and vibrate at the one minute mark to indicate that treatment of that zone is complete. Only treat the acne zone(s) identified for treatment. 4. After treatment, wipe your device clean with a tissue, being careful to avoid the charging port. Spray the device and a second tissue lightly with rubbing alcohol and wipe again, remaining careful to avoid the charging port. 5. Store safely away from water, moisture or debris. |
| Ancillary Product and Application Instructions: Objective: | Electroconductive Media Apply as a thin layer to all facial areas afflicted with acne The objective of this study is to demonstrate the safety and efficacy of a novel direct |
| Objective. | current device employed in the treatment of mild to moderate inflammatory acne after 12 weeks of every other day use. |
| Design: | Male and female subjects will be enrolled in this single-site monadic study to evaluate the effect of a device on acne treatment. Subjects who sign the consent form and meet all inclusion criteria and none of the exclusion criteria will be enrolled at the baseline visit. Subjects will be asked to continue use of their self-selected moisturizer, non-medicated cleanser, and sunscreen they have used without difficulty for the prior 30 days and for the 12-week study. Subjects must also continue all facial products and cosmetics unchanged for the duration of the study. No other oral or topical acne products can be used. Subjects must be washed out of all topical acne products for at least 2 weeks and all oral acne products for at least 4 weeks prior to study participation. Subjects must possess mild to moderate acne with 5-30 inflammatory lesions and no nodules/cysts. |

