- 4. Turn on your device by pressing the button at the top. You will hear one beep.
- 5. Place the device on your skin. Lights will illuminate under the device when both silver probes come in contact with your skin. Both probes must keep contact with skin throughout treatment.
- 6. Slowly make continuous circles with the top probe (the one farthest away from the charging port) over acne within each facial zone. (You may feel a tingling sensation during treatment. That is normal.)
- 7. Treat each facial zone for 1 minute. Your device will beep and vibrate at the one minute mark to indicate that treatment of that zone is complete. Only treat the acne zone(s) identified for treatment.
- 8. At the end of treatment, your device will beep twice and turn off.

- 9. After treatment, wipe your device clean with a tissue, being careful to avoid the charging port. Spray the device and a second tissue lightly with rubbing alcohol and wipe again, remaining careful to avoid the charging port.
- 10. Store safely away from water, moisture or debris. After treatment, wipe your device clean with a tissue before putting it away.
- 11. Repeat treatment of the original acne zone(s) through the study. Perform treatments every other day for 12 weeks.
- 12. If any new areas of acne develop later in the study, you may also treat those additional zones until study completion. For example, if you have acne in the forehead and mouth zones at the start of the study, treat those two zones for every treatment. If additional acne develops on the left cheek later in the study, treat the left cheek zone in addition to the mouth and forehead zones for all remaining treatments

CHARGING:

When you see the orange light flashing while using your device, it's time to charge. To charge, plug in the charging cable provided. The orange light will remain illuminated while charging. You will know that your device is completely charged when the orange light is no longer on.

CONTRAINDICATIONS

ZIIP should not be used in the following areas

- Breast area
- Directly on top of the eyelid
- Midline of neck (bone of neck)
- Groin area
- Do not use this device on patients who have a cardiac pacemaker, implanted defibrillator, or other implanted metallic or electronic device because this may cause electric shock

WARNINGS

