4. STUDY OBJECTIVE

The objective of this study is demonstrate the safety and efficacy of a novel direct current device in the treatment of mild to moderate inflammatory acne after 12 weeks of every other day use.

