5. STUDY DESIGN OVERVIEW

Male and female subjects will be enrolled in this single-site monadic study to evaluate the effect of a direct-current device on acne treatment. Subjects who sign the consent form and meet all inclusion criteria and none of the exclusion criteria will be enrolled at the baseline visit. Subjects will be asked to continue their self-selected moisturizer, non-medicated cleanser, and sunscreen they have used without difficulty for the prior 30 days and for the 12 week study. Subjects must also continue all facial products and cosmetics unchanged for the duration of the study. No other oral or topical acne products can be used. Subjects must be washed out of all topical acne products for at least 2 weeks and all oral acne products for at least 4 weeks. Subjects must possess mild to moderate acne with 5-30 inflammatory lesions and no nodules/cysts.

At baseline visit, subjects will receive the study acne device to be applied to the areas of the face afflicted by acne following cleansing, every other day. The dermatologist investigator will assess the face for the investigator global acne assessment (IGA) based on the following 5 point ordinal scale: 0=clear, 1=almost clear, 2=mild, 3=moderate, and 4=severe. In addition, the dermatologist investigator will perform an inflammatory and non-inflammatory lesion count. The dermatologist investigator will assess the tolerability of the device in terms of peeling, dryness, redness, and swelling on a 5-point ordinal scale (0=none, 1=minimal, 2=mild, 3=moderate, & 4=severe).

The subjects will assess device tolerability in terms of itching, burning, redness, and swelling. All assessments will be made on a 5-point ordinal scale (0=none, 1=minimal, 2=mild, 3=moderate, & 4=severe). Subjects will be given their diaries, study device, and electroconductive media and asked to return to the research center in 2 weeks. A reminder text will be sent to encourage compliance prior to the week 2 visit.

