7.1.5 STUDY MATERIAL ADMINISTRATION

All subjects will use the active ZIIP device as currently marketed. The ZIIP Device will be customized for the delivery of acne treatment with -400 microamps direct current, applied 3 days per week on non-consecutive days, on each facial zone afflicted by acne. A electroconductive media will be applied to each facial zone afflicted by acne prior to initiation of the device treatment.

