7.2 STUDY CONDUCT PROCEDURES

7.2.1 BASELINE

Male and female subjects will be enrolled in this single-site monadic study to evaluate the effect of a direct current device on acne treatment. Subjects who sign the informed consent form and meet all inclusion criteria and none of the exclusion criteria will be enrolled at the baseline visit. Subjects will be asked to continue their self-selected moisturizer, nonmedicated cleanser, and sunscreen they have used without difficulty for the prior 30 days and for the 12 week study. Subjects must also continue all facial products and cosmetics unchanged for the duration of the study. No other oral or topical acne products can be used. Subjects must be washed out of all topical acne products for at least 2 weeks and all oral acne products for at least 4 weeks. Subjects must possess mild to moderate acne with 5-30 inflammatory lesions and no nodules/cysts.

At baseline visit, the dermatologist investigator will assess the face for the investigator global acne assessment (IGA) based on the following 5 point ordinal scale: 0=clear, 1=almost clear, 2=mild, 3=moderate, and 4=severe. In addition, the dermatologist investigator will perform an inflammatory and noninflammatory lesion count within each facial quadrant (zone). The subjects will then be provided the study device and electroconductive media for every other day use after cleansing to the acne afflicted facial zones. The first use of the device will occur at the research center to ensure all subjects are using the device properly.

The dermatologist investigator will assess the tolerability of the device in terms of peeling, dryness, redness, and swelling on a 5-point ordinal scale (0=none, 1=minimal, 2=mild, 3=moderate, and 4=severe). The subjects will then assess device tolerability in terms of itching, burning, redness, and swelling. All assessments will be made on a 5-point ordinal scale (0=none, 1=minimal, 2=mild, 3=moderate, and 4=severe). Subjects will be given their diaries and asked to return to the research center in 2 weeks. A reminder text will be sent to encourage compliance prior to the week 2 visit.

All investigator selected subjects will be photographed with the Canfield VISIA CR using Standard 1 lighting at baseline, week 2, week 4, and week 8, and week 12.

7.2.2 WEEK 2

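### The protocol gives two treatment schedules, 3 days per week and every other day, that no subject can both follow, so it is unclear which regimen the week-12 result describes

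*Combined protocol and SAP*

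**What the plan says.** The frequency of device use is stated in two ways.

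*Three non-consecutive days a week:*
- Synopsis, test device row: "applied 3 days per week on non-consecutive days, on all areas afflicted by acne"
- Section 7.1.5: "400 microamps direct current, applied 3 days per week on non-consecutive days, on each facial zone afflicted by acne"
- Section 10.3: "applied 3 days per week on non-consecutive days, on all facial zones afflicted by acne"

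*Alternate days:*
- Synopsis, objective: "inflammatory acne after 12 weeks of every other day use"
- Synopsis, subject device instructions, item 11: "Perform treatments every other day for 12 weeks"
- Section 4: "mild to moderate inflammatory acne after 12 weeks of every other day use"
- Section 5: "areas of the face afflicted by acne following cleansing, every other day"
- Section 7.2.1: "study device and electroconductive media for every other day use after cleansing to the acne afflicted facial zones"
- The Synopsis design text, the Synopsis efficacy endpoint and Section 12.5 also specify alternate-day use.

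The Synopsis therefore carries both schedules. No section treats them as equivalent, gives one precedence, or states how many sessions a subject should complete. Section 8.1 takes compliance from the diary sheets without giving an expected count.

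**The concern.** The sections that tell the site how to administer the device prescribe one regimen. The objective, the subject instruction and the efficacy endpoint name another. All subjects use the active device, so the study's result is a statement about one regimen, and a reader of the report could not tell from the protocol which regimen that was meant to be.

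Two practical matters follow. First, the diaries are checked at every return visit with no stated number of sessions to check them against, and the rest of the protocol supports two different numbers. Second, Section 14.5 allows no deviations from the protocol, and Section 9.1 lists protocol violation as a reason for discontinuation. Read literally, a subject who follows either schedule perfectly departs from the other.

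Exposure could also differ between subjects if site staff or the instructional video convey the three-day wording. This is a risk only, because the one subject instruction list that states a frequency gives alternate days.

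**Working it through.** The protocol states no total number of sessions, so there is no figure of its own to reproduce. The sessions can be counted directly.

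**Inputs**
- Treatment period: 12 weeks x 7 = 84 days (Synopsis; Section 9.1).
- First use at the baseline visit, taken as day 0 (Section 7.2.1).
- 1 minute per facial zone per session (Synopsis; Section 10.3).
- Visits at weeks 2, 4, 8 and 12 (Section 2).

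**Totals**
- Three days a week: 3 x 12 = 36 sessions.
- Alternate days: days 0, 2, ..., 82, which is 84 / 2 = 42 sessions. Counting day 84 as well gives 43.
- Difference: 42 - 36 = 6 sessions. As ratios, 42 / 36 = 1.167 and 36 / 42 = 0.857.
- Time per zone: 36 x 1 = 36 minutes against 42 x 1 = 42 minutes.

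**Can one subject meet both texts?** Counting weeks from first use, alternation gives 4, 3, 4, 3, ... sessions, so 6 of the 12 weeks hold four. Starting one day later only reverses the order (3, 4, 3, 4, ...). Choosing different week boundaries does not help: any 14 consecutive days of strict alternation contain 14 / 2 = 7 sessions, while two weeks at three per week contain 6. A check of every possible 14-day pattern found none with exactly three sessions in each week and treatment every second day. The schedules can coincide within a single week, but not across two consecutive weeks.

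**Expected diary entries by visit interval**

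| Interval | Days | 3 per week | Alternate days |
|---|---|---|---|
| Baseline to week 2 | 0-13 | 6 | 7 |
| Week 2 to week 4 | 14-27 | 6 | 7 |
| Week 4 to week 8 | 28-55 | 12 | 14 |
| Week 8 to week 12 | 56-83 | 12 | 14 |
| Total | 0-83 | 36 | 42 |

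**Effect on a compliance figure.** A subject with 36 sessions is at 36 / 36 = 100% on one text and 36 / 42 = 85.7% on the other. A subject with 42 sessions is at 42 / 42 = 100% or 42 / 36 = 116.7%.

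**The case against.** The strongest reply is that the endpoint is not itself ambiguous. Every statement of the objective and of the efficacy endpoint specifies alternate days, as does the only subject instruction list that gives a frequency. On this view the three administration statements are loose drafting, or alternate-day use is shorthand for a pattern such as Monday, Wednesday and Friday. The statistical consequence is also slight. The signed rank test on the week-12 IGA does not depend on the schedule, a single-arm study cannot become unbalanced between groups, and the protocol defines no per-protocol set or compliance threshold that would use 36 or 42 as a denominator.

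Much of this stands. The planned test is unaffected, the gap is modest, and unequal exposure is a possibility rather than a demonstrated fact. Neither the diary form nor the content of the video is in the documents, so what they convey about frequency is unknown.

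It does not remove the contradiction. Consistent endpoint wording does not settle which regimen was studied when Sections 7.1.5 and 10.3 prescribe a different one. No section supports the shorthand reading, and instruction 11 is explicit. It is fair to say that adding session counts to Section 8.1 goes beyond curing the inconsistency, so that part of the fix is optional.

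**Conclusion.** The concern holds. The frequency of the investigational treatment is stated in two incompatible ways in current protocol text, and nothing reconciles them. The size is 36 against 42 sessions over 84 days (43 if day 84 is treated), or 6 minutes per zone. The count assumes strict alternation from first use at baseline, and 3 days per week read as exactly three.

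The documents contain no dose-response information, so no effect on outcome is claimed, and the week-12 analysis is computed in the same way under either schedule. The point should nevertheless be corrected before enrolment, because it concerns what treatment the study tests and reports, and exposure recorded under conflicting instructions cannot be put right afterwards. This review takes no position on which schedule is correct.

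**What to change.** The sponsor should reconcile the passages to one schedule of its own choosing and use identical wording in:
- the Synopsis: device row, objective, design text, subject instructions and endpoint;
- Sections 4, 5, 7.1.5, 7.2.1, 10.3 and 12.5;
- the diary and any instruction sheet given to subjects.

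As a useful addition, Section 8.1 could state the planned number of sessions that follows from the chosen schedule, in total and per visit interval, so that the diary checks have a reference.

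The cost is a wording amendment before enrolment, with approval from the sponsor and the IRB as Section 14.5 requires, and a matching diary and instruction sheet. Visits, measures and the planned tests do not change.

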10.4 PACKAGING, LABELING, DISTRIBUTION

Study products will be dispensed in the packaging provided by the sponsor.

10.5 STORAGE AND ACCOUNTABILITY OF STUDY PRODUCT

The study product will be stored at room temperature, away from sunlight, in a locked, limited access area at the study site. Access to the study product will be limited to the investigator and staff members designated to dispense study medication. A study product log will be used to record the dispensation and return of all study products. The subject number/initials, and the initials and date of the person dispensing and receiving the returned study product will be documented on this form.

10.6

CODE DISCLOSURE

The study coordinator will not develop a code as all subjects will use the active device and electroconductive media in this monadic study.

